**Table 5-1. Planned Dosing Regimen**

Period	Screen	Initial Therapy												Continuing Therapy
Visit	1	2	3	4	5	6	7	8	9	10	11	12	13	14+
Week	-4	1	2	3	4	5	6	7	8	12	16	20	24	30+
Study Day	-28 Days	1	8	15	22	29	36	43	50	78	106	134	162	204+
Purpose	Screening	Clinic Visit	Clinic Visit	Clinic Visit	Clinic Visit	Clinic Visit	Clinic Visit	Clinic Visit	Clinic Visit	Clinic Visit	Clinic Visit	Clinic Visit	Clinic Visit	Clinic Visit
Idelalisib (Arm A)		-----150 mg BID or highest tolerated dose, taken continuously----->												
Pre-medications (Arms A and B)	Antipyretic	X	X	X	X	X	X	X	X	X	X	X	X	X
	Antihistamine	X	X	X	X	X	X	X	X	X	X	X	X	X
	Prednisolone	X a	X a	X b	X b	X b	X b	X b	X b	X b	X a	X c	X c	X c
Ofatumumab, mg	Arm A	300	1000	1000	1000	1000	1000	1000	1000	1000	1000	1000	1000	1000
	Arm B	300	2000	2000	2000	2000	2000	2000	2000	2000	2000	2000	2000	2000

a Corticosteroid should be given at full dose (prednisolone 100 mg or equivalent).

b Corticosteroid may be given at gradually decreasing doses for successive infusions if a Grade  $\geq 3$  reaction did not occur with the preceding ofatumumab infusion.

c Corticosteroid dose (prednisolone doses of 50 mg to 100 mg or equivalent) may be given if a Grade  $\geq 3$  reaction did not occur with the preceding ofatumumab infusion.

**Abbreviation:** BID=twice per day

### 5.3.2. Investigational Study Drug (Idelalisib)

#### 5.3.2.1. Premedication

No specific premedications or supporting medications are required in conjunction with idelalisib administration.

In the absence of concomitant cytotoxic administration, tumor lysis syndrome is uncommon with either idelalisib or ofatumumab. However, investigators are at liberty to consider additional monitoring and prophylaxis for tumor lysis syndrome according to local practices.

#### 5.3.2.2. Administration Instructions

The prescribed dose of idelalisib should be taken orally. At each dose administration, the tablet number corresponding to the appropriate dose of study drug is to be swallowed whole with 100 to 200 mL (~ 4 to 8 ounces) of water. In case of breakage of the tablets in the oral cavity, additional water should be taken as a rinse.

Study drug may be taken with or without food. There are no known dietary restrictions related to study drug use.

#### 5.3.2.3. Dosing Schedule

Idelalisib will be started on a BID schedule beginning ~30 minutes prior to the initial ofatumumab infusion. Study drug should be taken at approximately the same times each day. Ideally, doses should be taken at ~12-hour intervals (eg, at ~7 AM and at ~7 PM). While it is realized that variations in dosing schedule may occur in the outpatient setting, the prescribed regimen should be followed as closely as possible, especially in the clinic.

At specified clinic visits, the study drug will be administered in the clinic with dosing appropriately timed relative to blood sampling for idelalisib pharmacokinetics. As detailed in Section 6.2, clinic staff should record idelalisib administration information, including the exact clock time of each dose, for doses of study drug administered in the clinic or hospital. Thereafter, subjects will be given an adequate supply of tablets to take at home.

#### 5.3.2.4. Dose Levels

Idelalisib dose levels are shown in Table 5-2 below. The starting dose level will be 150 mg BID. The lower dose level (Dose Level -1) is provided in case a subject requires a study drug dose modification.

**Table 5-2. Idelalisib Dose Levels**

Dose Level	Dosing Regimen
Starting	150 mg BID
-1	100 mg BID

**Abbreviation:** BID=twice per day

### 5.3.2.5. Dose Schedule Interruptions and Vomited Doses

Subjects who have a delay in administration of a dose of idelalisib of < 6 hours should take the planned dose as soon as possible after the intended time of administration. For subjects who have a delay in administration of study drug of  $\geq 6$  hours, the dose should not be taken. Study drug administration may continue but the missed dose should not be made up and the planned timing of subsequent study drug dosing should not be altered.

Vomited doses may be retaken, but only if the tablet is visible in the vomitus.

### 5.3.3. Ofatumumab

#### 5.3.3.1. Premedications

Before administration of ofatumumab, subjects must be premedicated to reduce the incidence and severity of infusion reactions. Although institution-specific standards may be followed, a recommended regimen is an oral antipyretic (acetaminophen [paracetamol], 1,000 mg or equivalent); an oral or intravenous antihistamine (cetirizine, 10 mg or equivalent); and an intravenous corticosteroid (prednisolone, 100 mg or equivalent). All premedications should be given ~30 to ~60 minutes prior to each ofatumumab administration. Local practices may be followed.

For the 1st, 2nd, and 9th ofatumumab infusions, intravenous corticosteroid at full dose (prednisolone, 100 mg or equivalent) should be administered. For the 3rd through 8th ofatumumab infusions, the corticosteroid dose may be gradually reduced prior to successive infusions if a Grade  $\geq 3$  reaction did not occur with the preceding ofatumumab infusion. For the 10th through 12th ofatumumab infusions, reduced corticosteroid doses (prednisolone doses of 50 mg to 100 mg) may be administered if a Grade  $\geq 3$  reaction did not occur with the prior infusion.

In the absence of concomitant cytotoxic administration, tumor lysis syndrome is uncommon with either idelalisib or ofatumumab. However, investigators are at liberty to consider additional monitoring and prophylaxis for tumor lysis syndrome according to local practices.

Institution of antibiotic prophylaxis for *Pneumocystis (carinii) jiroveci* is required for all subjects, and should be continued for up to 12 months following treatment with ofatumumab, particularly in patients with multiple risk factors for pneumocystis infection {[Green 2007](#)}.

#### 5.3.3.2. Administration Instructions

The recommended initial infusion rate for the first dose of ofatumumab is 12 mL/hour. Subsequent infusions can be initiated at 25 mL/hour. In the absence of infusion toxicity, the infusion rate can be increased as described in [Table 5-3](#). Ofatumumab should not be administered as an intravenous push or bolus. Infusion rates should not exceed the indicated values.

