#### 5.2.2.5. Solution Preparation and Dispensing

The clinic staff (eg, pharmacist or other qualified person) will be responsible for preparing ofatumumab. A qualified person (eg, nurse or physician with experience in monitoring the administration of chemotherapeutic agents) will be responsible for infusing ofatumumab.

Before use, the ofatumumab vials should be visually inspected for particulate matter and discoloration. The solution should be colorless and may contain a small amount of visible translucent-to-white, amorphous, ofatumumab particles. The solution should not be used if discolored or cloudy, or if foreign particulate matter is present.

For the preparation of each 300-mg dose of ofatumumab, 15 ml should be withdrawn from a 1,000-mL polyolefin or PVC bag of 0.9% Sodium Chloride Injection, USP and discarded, and 5 mL from each of 3 vials containing 100 mg/5 mL of ofatumumab should be aseptically added to the bag.

For the preparation of each 1,000-mg dose of ofatumumab, 50 ml should be withdrawn from a 1,000-mL polyolefin or PVC bag of 0.9% Sodium Chloride Injection, USP and discarded, and 50 mL from a vial containing 1000 mg/50mL of ofatumumab should be aseptically added to the bag.

For the preparation of each 2,000-mg dose of ofatumumab, 100 ml should be withdrawn from a 1,000-mL polyolefin or PVC bag of 0.9% Sodium Chloride Injection, USP and discarded, and 50 mL from each of 2 vials containing 1000 mg/50 mL of ofatumumab should be aseptically added to the bag.

The diluted solution should be mixed by gentle inversion. The infusion solution should not be mixed or diluted with other drugs.

Using an infusion pump, ofatumumab should be administered via polyvinyl chloride administration sets and through an in-line filter. The intravenous line should be flushed with 0.9% Sodium Chloride Injection, USP before and after each dose.

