**Table 5-3. Study Drug (Ofatumumab) Infusion Rates**

Interval After Start of Infusion, min	Arm A		Arm B		
	Infusion 1 (300 mg), ml/hr	Infusion 2-12 (1,000 mg), ml/hr	Infusion 1 (300 mg), ml/hr	Infusion 2 (2,000 mg), ml/hr	Infusion 3-12 (2,000 mg), ml/hr
0-30	12	25	12	12	25
31-60	25	50	25	25	50
61-90	50	100	50	50	100
91-120	100	200	100	100	200
> 120	200	400	200	200	400

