### 5.3.3.3. Management of Infusion Toxicity

Ofatumumab can cause infusion reactions manifesting as bronchospasm, dyspnea, laryngeal edema, pulmonary edema, flushing, hypertension, hypotension, syncope, cardiac ischemia/infarction, back pain, rigors, abdominal pain, pyrexia, rash, urticaria, and angioedema {[Coiffier 2008](#), [Glaxo Group Limited 2011](#), [Wierda 2010](#)}. Reactions are typically more frequent and severe during the first infusion and are generally less frequent and less severe with subsequent infusions. In the Phase 2 pivotal trial {[Wierda 2010](#)}, infusion reactions occurred in 44% of patients on the day of the first infusion (300 mg), in 29% of patients on the day of the second infusion (2,000 mg), and less frequently during subsequent infusions. The time to onset of infusion toxicity may range from 30 to 120 minutes.

Subjects should be monitored (including vital signs approximately every 15 minutes) for infusion toxicity for ~1 hour following the administration of the first and second infusions, or until vital signs return to normal or baseline for subjects who experience infusion toxicity during any infusion. If a subject has not experienced infusion toxicity during the first 2 infusions, it is acceptable to perform a final vital signs check 15 to 30 minutes after the end of subsequent infusions.

Patients with pre-existing pulmonary or cardiac conditions, those who experienced prior cardiopulmonary adverse reactions to ofatumumab, and those with high numbers of circulating malignant cells ( $\geq 25 \times 10^9/L$ ) may be at particular risk. For example, in a study of patients with moderate to severe chronic obstructive pulmonary disease, 2 of 5 patients developed Grade 3 bronchospasm during infusion {[Glaxo Group Limited 2011](#)}.

If an infusion reaction Grade  $\leq 2$  occurs, the infusion may be temporarily slowed or interrupted and then can be restarted when the subject's condition has stabilized. Upon restarting, the infusion rate should be half of the infusion rate at the time the infusion was paused but not less than 12 mL/hour. After resuming the infusion, the infusion rate may be increased consistent with [Table 5-3](#) based on patient tolerance.

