If an infusion reaction Grade  $\geq 3$  occurs, the infusion must be interrupted. Medical management (eg, oxygen, epinephrine, bronchodilators, and/or glucocorticoids) should be instituted, as needed. After the severity of the reaction has decreased to Grade  $\leq 2$  the investigator may restart the infusion at the initial rate for this ofatumumab dose (ie, at 12 mL/hour or 25 mL/hour).

If the severity of the infusion reaction does not rapidly resolve to Grade  $\leq 2$  despite adequate clinical intervention, or if infusion reactions of Grade  $\geq 3$  occur on 3 occasions during a single infusion, the subject may be withdrawn from ofatumumab treatment at the discretion of the investigator. If the subject is being treated on Arm A of the study, the subject should continue idelalisib if the subject is tolerating idelalisib therapy.

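### Section 5.3.3.2 lets every infusion after the first start at 25 mL/hour, but Table 5-3 starts Arm B infusion 2, the first 2,000-mg dose, at 12 mL/hour

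*Protocol*

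**What the plan says.** Protocol Section 5.3.3.2 gives two starting rates. For the first infusion: "The recommended initial infusion rate for the first dose of ofatumumab is 12 mL/hour". For all later ones: "Subsequent infusions can be initiated at 25 mL/hour". Neither sentence distinguishes the arms. The paragraph then refers to Table 5-3 for escalation ("In the absence of infusion toxicity, the infusion rate can be increased as described in" that table) and closes with a ceiling: "Infusion rates should not exceed the indicated values".

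Table 5-3 has five columns: two for Arm A (infusion 1; infusions 2-12) and three for Arm B (infusion 1; infusion 2; infusions 3-12). The column headed "Infusion 2 (2,000 mg), ml/hr" starts at 12 mL/hour and follows the infusion 1 schedule.

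Section 5.3.3.3 covers severe reactions. Once a Grade 3 or higher reaction has subsided to Grade 2 or lower, the investigator "may restart the infusion at the initial rate for this ofatumumab dose (ie, at 12 mL/hour or 25 mL/hour").

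**The concern.** The two starting-rate sentences divide infusions into the first and all the rest. Table 5-3 divides them differently in Arm B, where the second infusion keeps the slower schedule of the first. A site that takes its starting rate from the sentence will exceed the tabulated rate for Arm B infusion 2, and so break the ceiling stated in the same paragraph.

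This infusion is the first 2,000-mg dose, because infusion 1 is 300 mg in both arms. Section 5.3.3.3 reports that in the Phase 2 pivotal trial reactions occurred in 29% of patients on the day of the second (2,000 mg) infusion. The protocol also asks for full-dose corticosteroid before it (Section 5.3.3.1) and monitoring "for infusion toxicity for ~1 hour following the administration of the first and second infusions".

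There is a smaller statistical consequence. Section 9.4.2.4 compares infusion-reaction severity and infusion duration between arms, concentrating on the first two infusions. Arm B infusion 2 is the Day 8 control infusion in that comparison. If sites among the roughly 115 planned centers read the instruction differently, the comparison picks up avoidable variation.

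**Working it through.** **Text against table, starting rate (0-30 minutes)**

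| Column of Table 5-3 | Table, mL/hour | Section 5.3.3.2 text, mL/hour | Agree? |
|---|---|---|---|
| Arm A, infusion 1 (300 mg) | 12 | 12 | yes |
| Arm A, infusions 2-12 (1,000 mg) | 25 | 25 | yes |
| Arm B, infusion 1 (300 mg) | 12 | 12 | yes |
| Arm B, infusion 2 (2,000 mg) | 12 | 25 | **no** |
| Arm B, infusions 3-12 (2,000 mg) | 25 | 25 | yes |

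Each row of rates has five values under five labelled columns, and 1,000 mg appears only under Arm A and 2,000 mg only under Arm B. The mismatch is therefore not a misreading of a broken table.

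**Concentration (Section 5.2.2.5)**

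"For the preparation of each 2,000-mg dose of ofatumumab, 100 ml should be withdrawn from a 1,000-mL polyolefin or PVC bag" and replaced by 50 mL from each of two 1,000-mg vials, so 2,000 mg / 1,000 mL = 2 mg/mL. The 1,000-mg dose is made up the same way with one vial: 1,000 mg / 1,000 mL = 1 mg/mL.

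**Starting rate in mg/hour (rate × concentration)**

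- Arm B infusion 2, table: 12 × 2 = 24 mg/hour.
- Arm B infusion 2, text: 25 × 2 = 50 mg/hour. Ratio 50 / 24 = 2.08.
- Arm A infusion 2, text and table: 25 × 1 = 25 mg/hour.

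The tabulated 24 mg/hour nearly matches Arm A's 25 mg/hour at the same infusion, which suggests that the separate column was deliberate.

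**First 30 minutes, Arm B infusion 2**

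- Table: 0.5 × 12 = 6 mL = 12 mg.
- Text: 0.5 × 25 = 12.5 mL = 25 mg.
- Difference: 6.5 mL = 13 mg.

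**Total time for 1,000 mL, Arm B infusion 2**

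- Infusion 2 column throughout: 0.5 × (12 + 25 + 50 + 100) = 93.5 mL in 2 h; 906.5 / 200 = 4.53 h more; total 6.53 h.
- Start at 25, then the infusion 2 column: 0.5 × (25 + 25 + 50 + 100) = 100 mL in 2 h; 900 / 200 = 4.50 h more; total 6.50 h. Difference 0.0325 h, or 1.95 minutes.
- Start at 25 and stay in the infusions 3-12 column: 0.5 × (25 + 50 + 100 + 200) = 187.5 mL in 2 h; 812.5 / 400 = 2.03 h more; total 4.03 h. This is about 2.5 h shorter, with a peak of 400 × 2 = 800 mg/hour against 200 × 2 = 400 mg/hour.

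**Restart after a Grade 3 or higher reaction**

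Section 5.3.3.3 ties the restart to the initial rate for the dose in question and offers 12 or 25 mL/hour. If dose means strength, the 2,000-mg strength has both values in Table 5-3: 12 for infusion 2 and 25 for infusions 3-12. If dose means the infusion in progress, its initial rate is 12 by the table and 25 by the text. Neither reading settles the restart rate for Arm B infusion 2.

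**The case against.** The best answer is that the paragraph largely corrects itself. The 25 mL/hour sentence is permissive, the ceiling sentence follows shortly after it, and a table specific to arm and infusion should override a general statement. Read this way, 12 mL/hour applies and only loose wording remains. This does show which value is intended, and a careful site would probably use it. It does not remove the conflict: the text sends the reader to the table for increases and states its own starting rate, and a permissive sentence still permits what the table rules out.

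On the restart, the protocol does use dose to mean an administration elsewhere, including in Section 5.3.3.2 itself. That reading is natural, but it only carries the original conflict forward. The restart problem is best seen as a consequence of the first, not a separate defect.

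Three points of scale stand. The hour of monitoring applies to the first two infusions in both arms, so it is no special signal about Arm B infusion 2. Table 5-3 itself moves this infusion to 25 mL/hour at minute 31 and allows a 25 mL/hour start for the same strength from infusion 3. And the 4.03-hour path requires ignoring the infusion 2 column at every later step, whereas the sentence governs only how an infusion begins.

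**Conclusion.** The concern holds. Section 5.3.3.2 and Table 5-3 give different starting rates for one infusion, Arm B infusion 2: 25 against 12 mL/hour, or 50 against 24 mg/hour. The excess is 13 mg in the first 30 minutes. The effect on total duration depends on what the site does next: about 2 minutes if it rejoins the infusion 2 column, which is the more plausible path, and up to about 2.5 hours if it adopts the infusions 3-12 column throughout. These figures assume the 1,000-mL preparation in Section 5.2.2.5 and no interruptions.

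This is an internal contradiction in an operative dosing instruction and should be corrected. It has no bearing on PFS, sample size or error control. Its only analytic reach is the infusion-reaction comparison in Section 9.4.2.4.

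**What to change.** In Section 5.3.3.2, add to the 25 mL/hour sentence: *except infusion 2 in Arm B (2,000 mg), which starts at 12 mL/hour as in Table 5-3*.

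In Section 5.3.3.3, replace the parenthesis offering 12 or 25 mL/hour with: *the 0-30 minute rate in Table 5-3 for that arm and infusion*.

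The cost is one sentence and one parenthesis. Table 5-3 stays as it is, and no design element or analysis changes.

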**Table 5-3. Study Drug (Ofatumumab) Infusion Rates**

Interval After Start of Infusion, min	Arm A		Arm B		
	Infusion 1 (300 mg), ml/hr	Infusion 2-12 (1,000 mg), ml/hr	Infusion 1 (300 mg), ml/hr	Infusion 2 (2,000 mg), ml/hr	Infusion 3-12 (2,000 mg), ml/hr
0-30	12	25	12	12	25
31-60	25	50	25	25	50
61-90	50	100	50	50	100
91-120	100	200	100	100	200
> 120	200	400	200	200	400

### 5.3.3.3. Management of Infusion Toxicity

Ofatumumab can cause infusion reactions manifesting as bronchospasm, dyspnea, laryngeal edema, pulmonary edema, flushing, hypertension, hypotension, syncope, cardiac ischemia/infarction, back pain, rigors, abdominal pain, pyrexia, rash, urticaria, and angioedema {[Coiffier 2008](#), [Glaxo Group Limited 2011](#), [Wierda 2010](#)}. Reactions are typically more frequent and severe during the first infusion and are generally less frequent and less severe with subsequent infusions. In the Phase 2 pivotal trial {[Wierda 2010](#)}, infusion reactions occurred in 44% of patients on the day of the first infusion (300 mg), in 29% of patients on the day of the second infusion (2,000 mg), and less frequently during subsequent infusions. The time to onset of infusion toxicity may range from 30 to 120 minutes.

Subjects should be monitored (including vital signs approximately every 15 minutes) for infusion toxicity for ~1 hour following the administration of the first and second infusions, or until vital signs return to normal or baseline for subjects who experience infusion toxicity during any infusion. If a subject has not experienced infusion toxicity during the first 2 infusions, it is acceptable to perform a final vital signs check 15 to 30 minutes after the end of subsequent infusions.

Patients with pre-existing pulmonary or cardiac conditions, those who experienced prior cardiopulmonary adverse reactions to ofatumumab, and those with high numbers of circulating malignant cells ( $\geq 25 \times 10^9/L$ ) may be at particular risk. For example, in a study of patients with moderate to severe chronic obstructive pulmonary disease, 2 of 5 patients developed Grade 3 bronchospasm during infusion {[Glaxo Group Limited 2011](#)}.

If an infusion reaction Grade  $\leq 2$  occurs, the infusion may be temporarily slowed or interrupted and then can be restarted when the subject's condition has stabilized. Upon restarting, the infusion rate should be half of the infusion rate at the time the infusion was paused but not less than 12 mL/hour. After resuming the infusion, the infusion rate may be increased consistent with [Table 5-3](#) based on patient tolerance.

If an infusion reaction Grade  $\geq 3$  occurs, the infusion must be interrupted. Medical management (eg, oxygen, epinephrine, bronchodilators, and/or glucocorticoids) should be instituted, as needed. After the severity of the reaction has decreased to Grade  $\leq 2$  the investigator may restart the infusion at the initial rate for this ofatumumab dose (ie, at 12 mL/hour or 25 mL/hour).

If the severity of the infusion reaction does not rapidly resolve to Grade  $\leq 2$  despite adequate clinical intervention, or if infusion reactions of Grade  $\geq 3$  occur on 3 occasions during a single infusion, the subject may be withdrawn from ofatumumab treatment at the discretion of the investigator. If the subject is being treated on Arm A of the study, the subject should continue idelalisib if the subject is tolerating idelalisib therapy.

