Grade 3 (ALT/AST>5-20xULN) (Bilirubin>3-10xULN)	Withhold idelalisib. Monitor ALT, AST, ALP, and bilirubin at least 1x per week until all abnormalities are Grade ≤ 1. If bilirubin abnormality was Grade < 3, resume idelalisib at same dose level. If bilirubin abnormality was Grade ≥ 3, resume idelalisib at lower dose level.	Delay ofatumumab as necessary to ensure subject is sufficiently stable to receive further treatment; thereafter maintain full dose and schedule.
Grade 4 (ALT/AST>20xULN) (Bilirubin>10xULN)	Withhold idelalisib. Monitor ALT, AST, ALP, and bilirubin at least 1x per week until all abnormalities are Grade ≤ 1. If bilirubin abnormality was Grade < 4, resume idelalisib at lower dose level. If bilirubin abnormality was Grade 4, discontinue idelalisib.	Delay ofatumumab as necessary to ensure subject is sufficiently stable to receive further treatment; thereafter maintain full dose and schedule.
Pneumonitis (with new onset or worsening of baseline, dyspnea, cough, or hypoxia without obvious infectious cause)		
Grade 1 (asymptomatic)	Withhold idelalisib until resolution to baseline. May resume at lower dose level or discontinue study drug at investigator discretion.	Maintain current dose level and schedule.
Grade ≥ 2	Discontinue idelalisib permanently in subjects with any severity of symptomatic pneumonitis and institute therapy as clinically appropriate.	Delay ofatumumab as necessary to ensure subject is sufficiently stable to receive further treatment; thereafter maintain full dose and schedule.
Other Nonhematological Adverse Events		
Grade ≤ 2	Maintain current dose level and schedule	Maintain current dose level and schedule.
Grade ≥ 3	Withhold idelalisib until Grade ≤ 1. May resume idelalisib at initial or lower dose level or discontinue idelalisib at investigator discretion.	Delay ofatumumab as necessary to ensure subject is sufficiently stable to receive further treatment; thereafter maintain full dose and schedule or discontinue ofatumumab at investigator discretion.
Pneumocystis jirovecii pneumonia (PJP)		
Any Grade	Discontinue idelalisib permanently	

NCI CTCAE Grade	Recommendations and Required Action (in italics)	
	Idelalisib	Ofatumumab
Organizing Pneumonia		
Any Grade	Discontinue idelalisib permanently	
CMV infection/reactivation		

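### Section 5.3.3.3: on ofatumumab infusions that start at 25 mL/h, a pause at 25 mL/h restarts at 12.5 mL/h after a Grade ≤2 reaction but may restart at 25 mL/h after a Grade ≥3 reaction

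*Protocol*

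**What the plan says.** Section 5.3.3.3 of the protocol separates infusion reactions by grade.

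- **Grade ≤2.** Intervention is optional: "the infusion may be temporarily slowed or interrupted". If the infusion was paused, then on restarting "the infusion rate should be half of the infusion rate at the time the infusion was paused", with a floor of 12 mL/h.
- **Grade ≥3.** Interruption is mandatory, with medical management as needed. Once severity has dropped to Grade ≤2, "the investigator may restart the infusion at the initial rate for this ofatumumab dose (ie, at 12 mL/hour or 25 mL/hour"). Withdrawal from ofatumumab is an option if the reaction does not resolve quickly to Grade ≤2, or if Grade ≥3 reactions occur three times within one infusion.

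Table 5-3 fixes the initial rates. Infusion 1 starts at 12 mL/h in both arms. In Arm A, the column "Infusion 2-12 (1,000 mg), ml/hr" starts at 25 mL/h. In Arm B, infusion 2 (2,000 mg) starts at 12 mL/h, and the column "Infusion 3-12 (2,000 mg), ml/hr" starts at 25 mL/h. Section 5.3.3.2 makes these rates ceilings: "Infusion rates should not exceed the indicated values".

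**The concern.** A restart rule should be at least as cautious after a severe reaction as after a mild one. Here the two rules use different reference points: the Grade ≤2 rule halves the paused rate, and the Grade ≥3 rule returns to the starting rate. When the infusion is paused while still at its starting rate, returning to the start is no reduction at all, but halving is.

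A subject with a Grade ≥3 reaction at 25 mL/h may therefore resume at the rate at which that reaction occurred. A subject with a Grade 1 or 2 reaction at the same point is told to resume at half of it. The Grade ≥3 paragraph requires only a fall to Grade ≤2, not full resolution, so both subjects may have similar symptoms at restart.

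What is at stake is patient safety during infusion. The listed manifestations include bronchospasm, laryngeal edema and cardiac ischemia.

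**Working it through.** **Inputs**

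- Grade ≤2 restart (Section 5.3.3.3): max(12, paused rate / 2) mL/h.
- Grade ≥3 restart (Section 5.3.3.3): the initial rate, taken from the first row of the relevant Table 5-3 column.
- Rate steps (Table 5-3): 25, 50, 100, 200, 400 mL/h for Arm A infusions 2-12 and Arm B infusions 3-12. For infusion 1 in both arms and Arm B infusion 2: 12, 25, 50, 100, 200 mL/h.

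**Infusions that start at 25 mL/h**

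| Paused at (mL/h) | Grade ≤2 restart | Grade ≥3 restart permitted | Comparison |
|---|---|---|---|
| 25 | max(12, 12.5) = 12.5 | 25 | reversed, 25 / 12.5 = 2-fold |
| 50 | 25 | 25 | tied |
| 100 | 50 | 25 | Grade ≥3 stricter |
| 200 | 100 | 25 | Grade ≥3 stricter |
| 400 | 200 | 25 | Grade ≥3 stricter |

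One of the five steps is reversed and one is tied. A pause at 12.5 mL/h is not a Table 5-3 step, but it can be reached after one halving from 25. It gives max(12, 6.25) = 12 against 25, so it is reversed for the same reason.

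**Infusions that start at 12 mL/h**

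Pauses at 12, 25, 50, 100 and 200 mL/h give Grade ≤2 restarts of 12, 12.5, 25, 50 and 100. The Grade ≥3 restart is 12 throughout. The rules tie at the first step and nothing is reversed.

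**Which infusions are affected**

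- Arm A: every 1,000-mg infusion starts at 25 mL/h, so the initial rate for the dose is unambiguous. The reversed step exists on 11 of 12 infusions.
- Arm B: Table 5-3 gives two initial rates for 2,000 mg, 12 mL/h (infusion 2) and 25 mL/h (infusions 3-12). The Grade ≥3 rule refers to the dose, not the infusion, so it does not select one. Read per infusion, the reversed step exists on 10 of 12 infusions. If the 2,000-mg initial rate is read as 12 mL/h, it exists on none: a pause at 25 mL/h gives 12 against 12.5.

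**How the step is reached**

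The 25 mL/h rate runs in minutes 0-30. The protocol states: "The time to onset of infusion toxicity may range from 30 to 120 minutes". A first reaction at 25 mL/h therefore lies at or before the early edge of the stated window. The second route is a repeat reaction. A subject has a Grade ≥3 reaction at, say, 100 mL/h, restarts at 25, and reacts again before the first increase. The text again permits 25. Section 5.3.3.3 foresees repeat Grade ≥3 reactions within one infusion.

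**Time cost of a 12 mL/h restart on an infusion that starts at 25 mL/h**

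Assume the 30-minute steps of Table 5-3 are repeated after the restart and that enough volume remains to reach 400 mL/h.

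- Restart at 25: the four steps deliver (25 + 50 + 100 + 200) × 0.5 = 187.5 mL in 120 min. For 1,000 mL remaining, the total is 120 + (1,000 − 187.5) / 400 × 60 = 241.9 min.
- Restart at 12: the extra step takes 30 min and delivers 12 × 0.5 = 6 mL, which saves 6 / 400 × 60 = 0.9 min at the final rate. Net addition: 30 − 0.9 = 29.1 min.

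The net addition does not depend on the remaining volume as long as the final rate is reached.

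**The case against.** The strongest reply is that the protocol does escalate with severity. Grade ≥3 brings mandatory interruption, medical treatment and possible withdrawal. The premedication rules in Section 5.3.3.1 also tie steroid reduction at infusions 3-8 and 10-12 to the absence of a Grade ≥3 reaction at the preceding infusion. Table 5-4, under other nonhematological events of Grade ≥3, leaves room to stop: "thereafter maintain full dose and schedule or discontinue ofatumumab at investigator discretion". Returning to the starting rate is at least as cautious as halving at 50 mL/h and above. The restart itself is optional, the Table 5-3 rates are ceilings, and an investigator may go slower. The onset window makes the 25 mL/h step an unlikely place for a first reaction. Section 5.10 says the infusion-reaction recommendations agree with experience described in the product labeling.

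Most of this stands and limits the point to one step. It does not remove it. The ceiling for the first step is itself 25 mL/h, so the ceiling does not prevent the reversal. The text tells the investigator to slow down after the milder reaction and gives no such instruction after the severe one. The labeling statement gives a source, not a reason. The label is not available here. Section 5.10 also identifies 2,000 mg as the labeled dose and supports the 1,000-mg dose with other data, so the statement does not settle the Arm A case.

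A reader might infer that the protocol requires a faster restart after severe reactions, or that its Grade ≥3 rule is generally the laxer one. Neither is supported: the wording is permissive, and the rule is stricter at three of the five steps. Nor do 11 of 12 or 10 of 12 infusions measure risk. They count only where the step exists.

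**Conclusion.** The inconsistency is real, narrow and minor. On an infusion that starts at 25 mL/h and is paused at 25 mL/h, the directed restart after Grade ≤2 is 12.5 mL/h and the permitted restart after Grade ≥3 is 25 mL/h. For Arm A infusions 2-12 this follows from the text without interpretation. For Arm B infusions 3-12 it depends on reading the initial rate per infusion, which the wording leaves open. Nothing else in the protocol lowers the Grade ≥3 restart rate.

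The number of subjects exposed cannot be stated, because the protocol gives no frequency of Grade ≥3 reactions at 25 mL/h. It is expected to be small. Sample size, power, error rates and endpoints are untouched. The reason to act is that a written safety rule is less cautious for the more severe reaction in a situation the protocol itself can produce, and that one sentence removes it.

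**What to change.** In the Grade ≥3 paragraph of Section 5.3.3.3, replace the reference to the initial rate for the dose, including the parenthesis with the two rates, by: *at 12 mL/hour, with later increases following Table 5-3 as tolerated*.

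The Grade ≤2 restart is never below 12 mL/h, so a Grade ≥3 restart at 12 mL/h can never exceed it. The change does not loosen the rule on either reading of Arm B, and it removes the 12-or-25 ambiguity for 2,000 mg. A cap at the lower of the initial rate for the infusion and half the paused rate would be less suitable. It would settle Arm B infusions 3-12 on 25 mL/h where the text can now be read as 12, and it would clash with the 12 mL/h floor for pauses below 24 mL/h.

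The cost is one sentence, plus about 29 minutes net per restart on the assumptions above. The extra time falls on every Grade ≥3 restart of an infusion that starts at 25 mL/h, not only on those paused at 25 mL/h. The sponsor should check the wording against the ofatumumab label cited in Section 5.10.
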